1.2 RATIONALE

Despite improvements in the treatment of indolent lymphomas, the disease remains incurable. Thus, there is a continued need to improve treatment outcomes. The optimal treatment for newly diagnosed indolent lymphomas is based on tumor burden with options ranging from watchful waiting to single agent rituximab to chemoimmunotherapy regimens and most recently immunomodulator containing regimens.¹²⁻¹⁵ Very few prospective trials have been conducted in the low tumor burden subgroup of indolent lymphomas. The only trial in the rituximab era was a trial by Ardeshra et al wherein it was found that rituximab improved progression free survival, however, the study did not show any improvement in overall survival.²⁴ Based on previously described efficacy outcomes of single agent rituximab there is clearly ample scope to increase response rates and overall outcomes after front line therapy. Toward achieving the goals of improving outcomes in low tumor burden indolent lymphomas, we propose to use single agent ublituximab as induction therapy. Given the toxicity seen with standard combination treatment regimens in patients, an initial chemotherapy free regimen with a potent CD20 antibody such as ublituximab followed by a response driven addition of a chemotherapy-free targeted agent may be an attractive treatment option if found to be well tolerated and to have significant anti-tumor activity.

Patients who achieve responses less than a CR are usually followed with an expectant strategy or are treated with extended duration rituximab. It is obvious that these patients are at a high risk of progression. To date, there has not been much data-driven guidance on how to manage these "at-risk" patients until frank progression occurs. Treating these patients with novel targeted inhibitors has the potential to halt expected progression and thus, preclude these patients from the receipt of more toxic therapies at disease progression. Multiple targeted inhibitors are currently being tested in patients with lymphoma. The phosphatidylinositol-3-kinase (PI3K) pathway has an important role in many cellular functions, including B-cell antigen receptor signaling. Selective inhibition of PI3K isoform δ -dependent signaling has direct antitumor activity and exerts pleiotropic effects in the tumor microenvironment of B-cell malignancies, inducing apoptosis and reducing proliferation.³² Idelalisib, a first-in-class drug targeting the PI3K δ pathway, was approved for use in 2014 in the USA and the European Union after showing clinical activity in patients with relapsed or refractory CLL and FL.³³ Similar to other B-cell receptor inhibitors, idelalisib is administered indefinitely until disease progression or intolerable toxicities occur. However, studies documented unexpected life-threatening adverse events with this drug, including an increased risk of autoimmune complications (e.g., colitis, pneumonitis, and transaminitis) and infections (e.g., cytomegalovirus reactivation and *Pneumocystis jirovecii* pneumonia). These adverse events have driven the need for not only efficacious, but also safer therapies.

Umbralisib, as shown in the multiple studies above, is associated with low rates of immune-mediated toxicity and exhibits a favorable long-term tolerability profile at a median follow-up of 1.3 years, with up to 5 years of overall follow up. The mechanism for decreased immune-mediated toxicity is still being elucidated through ongoing pre-clinical and correlative studies examining umbralisib's selectivity for PI3K δ over PI3K γ , complimentary CK1 ϵ inhibition, and enhancement of regulatory T-cell function (Davids et al Abstract # PF444 EHA 2018).

In patients who do not achieve a CR, we propose to administer ublituximab plus umbralisib for a defined time duration (12 cycles) to assess if the addition of umbralisib can convert suboptimal responses to a CR. Ublituximab in combination with umbralisib is well tolerated and highly active in a broad population of heavily pretreated and high-risk patients with NHL and CLL.³² Most studies so far have been designed with fixed duration ublituximab and umbralisib being administered until progression or unacceptable toxicity. The unique feature of our proposed hypothesis is fixed duration administration of umbralisib with the hope of enhancing efficacy as well as mitigating toxicity.

Pastore et al have shown that a clinicogenetic risk model (m-7FLIPI) includes the mutation status of seven genes (*EZH2*, *ARID1A*, *MEF2B*, *EP300*, *FOXO1*, *CREBBP*, and *CARD11*), the FL International Prognostic Index (FLIPI), and the Eastern Cooperative Oncology Group (ECOG) performance status, improves risk stratification for failure-free survival (FFS) and overall survival in patients with FL receiving first-line immunochemotherapy.¹⁰ The utility of this risk model is unknown in patients with FL who have been previously untreated or treated with chemotherapy-free approaches. The correlative analysis will include identifying m-7FLIPI risk model for each FL, which can help predict CR rates to single and combination therapy.

2 POTENTIAL RISKS AND BENEFITS

2.1 POTENTIAL RISKS

SINGLE AGENT UBLITUXIMAB

Adverse Events and Potential Risks: The Investigator's Brochure (IB) is the primary source for safety information. The ublituximab IB includes a summary of adverse event data and discussion on potential risks that have been observed or may be predicted to occur with this study drug. Refer to the most recent IB, which is updated periodically, for current information on ublituximab.

UBLITUXIMAB + UMBRALISIB COMBINATION

Adverse Events and Potential Risks

Refer to the most recent Investigator's Brochures IBs for ublituximab and umbralisib, which are updated periodically, for current safety information on the combination of ublituximab and umbralisib.

SINGLE AGENT UMBRALISIB

Adverse Events and Potential Risks

The Investigator's Brochure (IB) is the primary source for safety information. The umbralisib IB includes a summary of adverse event data and discussion on potential risks that have been observed or may be predicted to occur with this study drug. Refer to the most recent IB, which is updated periodically, for current information on umbralisib.

2.2 KNOWN POTENTIAL BENEFITS

Ublituximab has demonstrated evidence of clinical activity in relapsed NHL's including relapsed FL and MZL. Ublituximab may increase the likelihood of improved responses as compared to rituximab in indolent lymphomas. Furthermore, this trial also studies the combination of ublituximab and umbralisib in patients who do not achieve a CR to single agent therapy. The combination of ublituximab and umbralisib has shown to be safe and efficacious in relapsed indolent lymphomas. This trial provides an opportunity to test this combination in patients who have a suboptimal response to ublituximab with the hope of improving outcomes. The risks to participants are reasonable in relation to the anticipated benefits to participants and/or society, and in relation to the importance of the knowledge that may reasonably be expected to result, thereby falling in favor of performing the study:

- To Participant: Potential to improve management and outcomes of malignancy
- To Society: Improved understanding of the role of Anti CD20 antibody and PI3K inhibitor in the management of indolent B cell NHL. Improved understanding of QOL assessments in indolent lymphomas
- Justify the importance of the knowledge gained: Anti-CD 20 antibody therapy and PI3K inhibitors have led to improved outcomes in patients with several subtypes of B-cell NHLs. However, there is a relative paucity of information regarding the efficacy of these agents as single agents or in combination in newly diagnosed indolent B-cell NHLs. This protocol will provide valuable insights into the potential role of these agents in the management of these lymphomas.

3 OBJECTIVES

Primary objectives:

To determine Best Complete response (CR) rates as measured by PET/CT scan at anytime during treatment with single agent or combination therapy

Secondary objectives:

- To determine overall response rates (ORR) in the entire cohort
- To assess safety and tolerability profile of single agent and combination therapy

[figure not shown]
Exploratory objectives:

- To determine ORR and CR rates after induction therapy in FL and MZL cohorts
- To determine ORR and CR rates after combination therapy in the entire FL and MZL cohorts
- To determine Partial response (PR), Stable disease (SD), progressive disease (PD) rate of single agent and combination therapy
- To assess duration of remission of single agent and combination therapy
- To assess 2-yr progression free survival (PFS) and overall survival (OS) of single agent and combination therapy
- To explore baseline disease and patient factors that may predict response to ublituximab alone and with umbralisib
- To assess rates of transformation to aggressive lymphoma
- To evaluate the health-related quality of life (QoL) of subjects as assessed by the following subject-reported questionnaire:
 - FACT-Lym, a standardized instrument for use as a measure of health-related QoL as highlighted in the **APPENDIX** section
- Correlative analysis: M7FLIPI testing at diagnosis may be performed which can help predict CR rates with single versus combination therapy. Patient samples will be tested in a CAP/CLIA-accredited laboratory on a custom next generation sequencing (NGS) panel. This panel consists of 310 genes, which are recurrently mutated across clonal hematopoietic proliferations including clonal hematopoiesis of indeterminate potential (CHIP), acute and chronic myeloid neoplasms, B- and T-cell lymphomas, and plasma cell neoplasms. Specifically included in this panel are the full coding sequences of the seven genes in the m7-FLIPI clinicopathologic riskmodel: *ARID1A*, *CARD11*, *CREBBP*, *EP300*, *EZH2*, *FOXO1*, and *MEF2B*. (Pastore et al. Lancet Oncol 2015).¹⁰ Mutation data will be analyzed by a board-certified molecular pathologist and these results will be incorporated with clinical data to determine the m7-FLIPI score.
- Minimal residual disease assessment may be performed on patient samples.

4 STUDY DESIGN AND ENDPOINTS

4.1 DESCRIPTION OF THE STUDY DESIGN

This is an open-label, Phase II interventional study in order to assess the safety and efficacy of single agent ublituximab as initial therapy for FL and MZL with response driven addition of umbralisib for suboptimal response.

Based on overall reporting in low tumor burden FL and MZL, CR rate of at least 30% was achieved when single agent rituximab was used in these subsets. We assume that by administering ublituximab (both as a single agent and in combination for individuals who fail to achieve a CR with the single agent), the CR rate will increase to 50%. Efficacy will be assessed using the proportion of patients treated with ublituximab alone or with ublituximab administered in combination who have a complete response. Thus, we will test the efficacy of ublituximab using a difference in proportions design by comparing an expected study population control rate of 50% to the comparison proportion being determined by the historical control CR rate of 30%. In other words, the null hypothesis is that the true response rate is 30%, and it will be formally tested against a one-sided alternative that the response rate is 50%.

A total of 24 patients will need to be accrued (assuming 73% power and a type I error of 0.10 when the true response rate is 50%). At study completion, the proportion of patients achieving a complete response will be calculated, along with 95% confidence intervals for this proportion. Assuming 20% screen fail/drop-out rate, 30 patients need to be screened for this study.

Patients will be followed for outcome measures up to 2 years from study enrollment. Study enrollment will continue until stopping endpoints. Of note, the study will accrue continuously, and will not stop enrollment of patients while analysis of stopping endpoints are underway.

Toxicity

Treatment-related mortality: If any patient experiences death due to an adverse event that is assessed as related to study treatment (by investigator and/or Sponsor), it will lead to temporary hold of study pending review by study team. The study will be terminated prematurely if at any point 2 patients experience treatment-related death secondary to the study regimen (Ublituximab and/or umbralisib)

Toxicities of special interest:

- a. Patients enrolled on the single agent treatment Ublituximab will be assessed for toxicities of special interest for 30 days. The study will be halted prematurely if more than 5 patients experience the following toxicities:
 - Grade 4 Neutropenia
 - Neutropenic Fever
- b. The combination arm of Ublituximab + Umbralisib is of special interest in this study. Patients enrolled on this arm will be assessed for toxicities of special interest for 90 days. The study will be halted prematurely if more than 3 consecutive patients enrolled on the combination arm experience any of the following toxicities:
 - Grade 3 or higher pneumonitis
 - Grade 3 or higher colitis
 - Grade 4 hepatitis
 - Grade 4 rash
 - Other grade 4 unmanageable events attributable to the study treatment.
- c. The study will be halted prematurely if a patient develops progressive multifocal leukoencephalopathy on single agent / combination arm of the study.

Patients will continue to receive study therapy as defined by the schema (4 weekly doses of ublituximab in the single agent treatment and ublituximab plus daily umbralisib for a total of 12 cycles in the combination arm) or until disease progression according to Cheson 2014, unacceptable toxicity, death due to an adverse event that is assessed as related to study treatment (by investigator and/or Sponsor), patient or physician decision to withdraw, or pregnancy, whichever occurs first. The study will end when all patients enrolled have completed planned treatment or the Sponsor decides to end the trial, whichever occurs first.

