5.5 PREMATURE TERMINATION OR SUSPENSION OF STUDY (STUDY STOPPING RULES)

Teleconferences will be held with the study sponsor to exchange findings and unexpected results that may occur in patients participating in this study. The study will be terminated based on toxicity stopping rules as discussed in section 8.5. Any new information suggesting the study intervention may be harmful in study population will be shared with the COMIRB. The principal investigator will discuss any such new information via conference with TG Therapeutics, Inc., and if warranted, may choose to terminate study.

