6.1.1 DOSING SCHEDULES

- 1) Patients with Stage II (non-contiguous), Stage III and Stage IV Follicular lymphoma and Marginal zone lymphoma will receive ublituximab 900 mg IV weekly for 4 doses (days 1, 8, 15 and 22)
- 2) At 8 weeks after completion of ublituximab monotherapy, patients will undergo PET-CT assessment.
- 3) Patients who do not achieve a CR after ublituximab monotherapy will receive a combination of ublituximab and umbralisib for a total of 12 cycles given as follows: ublituximab 900 mg IV on Days 1, 8 and 15 during the first cycle of combination treatment, on Day 1 of each subsequent 28-day cycle through Cycle 6 and then every 3 cycles (i.e. C9 and C12) PLUS umbralisib 800 mg PO daily on Days 1-28 of each 28-day cycle.

4) Patients with CR on either single or combination therapy will be followed with scans for 2 years.

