Grade 1 or 2	
Provide supportive care as warranted.
 
Stop all therapy and hold until complete resolution. Restart umbralisib at one lower dose level. Restart ublituximab at full dose.
 
If recurrence after re-challenge, discontinue umbralisib.
 
If applicable, hold ublituximab. Upon resolution, resume ublituximab at full dose and schedule.

Grade ≥ 3	
Provide supportive care as warranted.
 
Discontinue umbralisib and ublituximab.

*For sinopulmonary infections clearly not related to immune-mediated pneumonitis, umbralisib may be continued at investigator's discretion. While pneumonitis has been minimal with umbralisib, it is a reported adverse event associated with other PI3K delta inhibitors. Use of anti-pneumocystis and anti-herpetic viral prophylaxis is required prior to the start of therapy.
	
Liver Injury (ALT/SGPT, AST/SGOT, Bilirubin, Alkaline Phosphatase)	
Grade 1	
Maintain current umbralisib dose.
 
Assess concomitant medications and risk factors*.
 
Monitor labs every 1-2 weeks.
 
Maintain full dose and schedule of ublituximab, if applicable.***

NCI-CTCAE Grade	Dose Delay and/or Modification
Grade 2	
Maintain current umbralisib dose level. Assess concomitant medications and risk factors*. Begin supportive care (prednisone 0.5-1.0 mg/kg/day or equivalent per investigator discretion) **. Monitor labs at least weekly until Grade 1. Once resolved to Grade ≤ 1, taper prednisone by 10 mg per week until off.
 
Maintain full dose and schedule of ublituximab, if applicable.***
 
If liver toxicity recurs to Grade 2:
 
 ○ Re-initiate steroids. ○ Monitor labs at least weekly until Grade 1. ○ Consider delaying umbralisib. ○ If applicable, consider delaying ublituximab.*** ○ Once resolved to Grade ≤ 1 
 ○ If umbralisib was delayed, restart umbralisib at current dose. ○ If applicable: if ublituximab was delayed, restart ublituximab at full dose and schedule.*** ○ Taper prednisone by 10 mg per week until off.

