Diarrhea Grade \geq 3	
Provide supportive care as warranted.
 
Delay umbralisib until Grade \leq 2; thereafter, resume umbralisib at current dose or at next lower dose level at discretion of investigator
 
If recurrence after rechallenge, delay umbralisib until Grade \leq 1; thereafter, resume umbralisib at current dose or at next lower dose level at discretion of the investigator.
 
If umbralisib is delayed for $>$ 2 cycles at any time, discontinue umbralisib.
 
If applicable, delay ublituximab until \leq grade 2 (or until \leq grade 1 for recurrence after rechallenge); thereafter, resume ublituximab at full dose and schedule. If ublituximab is delayed for $>$ 2 cycles at any time, discontinue ublituximab.

NCI-CTCAE Grade	Dose Delay and/or Modification		
	Provide supportive care as warranted.		
Colitis (all Grades)	
Delay umbralisib. Treat with supportive care and after resolution of colitis, resume umbralisib at next lower dose level.
 
If umbralisib is delayed for > 2 cycles at any time, discontinue umbralisib.
 
If applicable, delay ublituximab until resolution; thereafter, resume ublituximab at full dose and schedule. If ublituximab is delayed for > 2 cycles at any time, discontinue ublituximab.
		
All Other Non-Hematological Adverse Events			
Grade \leq 2	
Maintain current dose level.
 
Provide supportive care as warranted.
		
Grade \geq 3	
Provide supportive care as warranted.
 
Delay umbralisib until Grade \leq 2; thereafter, resume umbralisib at current dose.
 
If recurrence after re-challenge, delay umbralisib until Grade \leq 2; thereafter, resume umbralisib at current dose or next lower dose level at discretion of the investigator.
 
If umbralisib is delayed for > 2 cycles at any time, discontinue umbralisib.
		
Umbralisib Dose Reduction Recommendations			
Study Drug	Starting Dose	1 st Dose Reduction	2 nd Dose Reduction
Umbralisib	800 mg	600 mg	400 mg

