8.6 SAFETY OVERSIGHT

Monitoring and Oversight

The sponsor investigator will be responsible for monitoring the trial per the trial monitoring plan, in addition to overseeing the safety and efficacy of the trial including any specimens collected, executing the data and safety monitoring (DSM) plan, and complying with all reporting requirements to local and federal authorities. This oversight will be accomplished through additional oversight from the Data and Safety Monitoring Committee (DSMC) at the University of Colorado Cancer Center (CU Cancer Center). The DSMC is responsible for ensuring data quality and study participant safety for all clinical studies at the CU Cancer Center, which is the coordinating institution of this trial.

A summary of the DSMC's activities is as follows:

- Conduct of internal audits
- Ongoing review of all serious adverse events (SAEs) and unanticipated problems (UAPs)
- May submit recommendations for corrective actions to the CU Cancer Center's Executive Committee

Per the CU Cancer Center Institutional DSM Plan, SAEs and UAPs are reported to the DSMC, IRB and the sponsor investigator per protocol. All SAEs and UAPs are to be reported to the DSMC within 7 (for fatal or life-threatening events) or 15 (non-life-threatening events) calendar days of the sponsor investigator receiving notification of the occurrence.

Each subject's treatment outcomes will be discussed by the site PI and appropriate staff at regularly scheduled meetings. Data regarding number of subjects, significant toxicities, dose modifications, and treatment responses will be discussed and documented in the meeting's minutes.

The sponsor investigator will provide a DSM progress report to the CU Cancer Center DSMC on a recurring basis (either every six or twelve months based on DSMC vote). The DSM report will

include a protocol summary; current enrollment numbers; summary of toxicity data to include specific SAEs, UAPs and AEs; any dose modifications; all protocol deviations; and protocol amendments. The DSM progress report submitted to the DSMC will also include, if applicable, the results of any efficacy data analysis conducted. Results and recommendations from the review of the progress report by the DSMC will then be provided to the sponsor investigator in a DSMC review letter. The sponsor investigator is then responsible for ensuring this letter is submitted to the site's IRB of record at the time of IRB continuing review.

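### The halting rule for combination toxicities counts 90 days of a planned 336-day course, so later non-fatal severe colitis or pneumonitis reaches no numeric halting rule

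*Combined protocol and SAP*

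**What the plan says.** Halting rule (b) appears in section 4.1 and again in section 8.5. On the combination arm, "Patients enrolled on this arm will be assessed for toxicities of special interest for 90 days". The trigger in section 4.1 follows: "The study will be halted prematurely if more than 3 consecutive patients enrolled on the combination arm experience any of the following toxicities". The list is Grade 3 or higher pneumonitis or colitis, Grade 4 hepatitis, Grade 4 rash, and other unmanageable Grade 4 events attributed to treatment. The start of the 90 days is not stated, and the trigger sentence has no time limit of its own.

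The course being monitored is much longer. Under section 6.1.1, patients not in CR after induction "will receive a combination of ublituximab and umbralisib for a total of 12 cycles", each of 28 days with daily umbralisib. Section 7.1 keeps patients who reach CR early on all 12 cycles.

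The other numeric rules have a different scope:

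- Rule (a) counts Grade 4 neutropenia and neutropenic fever during 30 days on single-agent treatment.
- Rule (c) counts progressive multifocal leukoencephalopathy only.
- The mortality rule has no time limit and terminates the study if "at any point 2 patients experience treatment-related death", but it counts only deaths.

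The non-numeric provisions do not expire. Under section 5.5 the principal investigator discusses new harm information with the drug supplier "and if warranted, may choose to terminate study". Under section 8.6 the DSMC reviews all SAEs as they occur. Table 3 in section 6.1.2 protects the individual patient: for Grade 3 or higher pulmonary toxicity it says "Discontinue umbralisib and ublituximab", and colitis of any grade interrupts treatment, then "after resolution of colitis, resume umbralisib at next lower dose level".

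**The concern.** A study-level halting rule should cover the exposure that carries the risk. This one stops counting after about a quarter of planned treatment, and no other numeric rule takes over for non-fatal events. Section 1.2 names colitis, pneumonitis and transaminitis among the life-threatening events seen with an earlier PI3K-delta inhibitor, so these are the toxicities the rule is meant to catch. The patients are previously untreated, and section 5.2 excludes those who need immediate chemotherapy-based cytoreduction.

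If severe immune-type toxicity proved frequent and tended to appear after the third cycle, the rule could stay silent. A halt would then depend on judgment, without a pre-stated count, for the remaining 246 planned treatment days.

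**Working it through.** **Calendar arithmetic**

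- Planned course: 12 × 28 = 336 days (sections 4.1 and 6.1.1).
- Share covered: 90/336 = 26.8%. Days not covered: 336 − 90 = 246.
- With the first combination dose as day 1, three cycles end on day 84, so day 90 is cycle 4 day 6.
- Adding the 30-day AE follow-up of sections 7.3.7 and 8.3 gives 336 + 30 = 366 days, of which 90 is 24.6%.

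**What the documents say about rate and onset.** Section 1.1.2(c) reports 75 patients on the combination: one biopsy-confirmed colitis, two pneumonitis, and Grade 3/4 ALT elevation in 3%. This gives (1 + 2)/75 + 3% = 7%. For these events the figure is high: no grade is given for the colitis or pneumonitis cases, and the rule requires Grade 4 hepatitis. Rash and other Grade 4 events are not included. No onset times are given for colitis or pneumonitis. For related events, diarrhea had a median onset of 21 days (range 1 to 838), and ALT/AST elevation of any grade a median of 55 days.

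**Assumptions.** 12 to 24 patients enter combination treatment. The 366-day event rate c is 7% (from above), 20% or 30% (both assumed). Three onset patterns are used, and the share of 366-day events falling in the first 90 days is:

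- Constant hazard: [1 − (1 − c)^(90/366)]/c = 0.253, 0.267 and 0.280 for c = 0.07, 0.20 and 0.30.
- Exponential onset with median m: [1 − 2^(−90/m)]/[1 − 2^(−366/m)] = 0.685 for m = 55 and 0.949 for m = 21.

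The per-patient probability p counted in 90 days is c times that share. The rule fires on four events in a row, so the firing probability is the exact chance of a run of at least 4 among n independent patients. Each cell gives n = 12 to n = 24.

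| Event rate c | 366-day count | 90 days, constant hazard | 90 days, median 55 | 90 days, median 21 |
|---|---|---|---|---|
| 7% | 0.020%–0.047% | 0.0001%–0.0002% | 0.005%–0.011% | 0.017%–0.038% |
| 20% | 1.18%–2.70% | 0.007%–0.016% | 0.28%–0.64% | 0.97%–2.21% |
| 30% | 5.31%–11.70% | 0.041%–0.096% | 1.31%–2.99% | 4.39%–9.73% |

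For example, at c = 0.30 with constant hazard, p = 0.30 × 0.280 = 0.084.

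**Would a later halt still help?** This was simulated at c = 0.30, with combination starts spread evenly over the two-year enrollment period and no early discontinuation. The rule fires on the first calendar day when four consecutively started patients all have a counted event. Ranges are again n = 12 to n = 24.

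| Onset | Fires before last start, 366-day count | Same, 90-day count | 366-day halts after all have started | Mean planned exposure left at a 366-day halt |
|---|---|---|---|---|
| Constant hazard | 2.7%–6.9% | 0.03%–0.09% | 50%–41% | 32%–36% |
| Median 55 days | 3.8%–9.1% | 1.1%–2.6% | 29%–22% | 49%–52% |
| Median 21 days | 4.4%–10.5% | 3.7%–8.9% | 17%–11% | 59%–63% |

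A halt under the longer count would therefore usually leave meaningful exposure to prevent, although some halts come after every combination patient has started.

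**The case against.** The strongest objection is materiality. At about 7%, the only rate the documents support and a high one for these events, rule (b) fires in at most 0.05% of trials even with full counting. The 20% and 30% rates are assumed. Both reported onset medians fall inside 90 days, and the 838-day value is the latest onset of all-grade diarrhea in a relapsed or refractory population treated without a fixed end. What makes the rule nearly inert is the requirement of four consecutive patients, which a longer window leaves in place. Late events are also not ignored: section 7.3.4 requires AE assessment and chemistry on day 1 of every cycle and monitoring for these toxicities, SAEs go to the drug supplier, the principal investigator and the DSMC, and the dose rules continue. Finally, because the trigger sentence has no time limit, it can be read as counting events at any time, in which case there is no gap.

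Much of this stands. The gain at the expected rate is negligible, and early onset removes most of it even at 30%. But a halting rule should almost never fire at the expected rate; its value is judged at rates that would be unacceptable, and there the 90-day limit can cost nearly all of its chance of firing. Discretionary review is a real safeguard but sets no threshold. On the unlimited reading, the 90-day sentence has no clear function, and the text should say so.

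**Conclusion.** The concern holds, as an inexpensive safety improvement of modest benefit. Rule (b) is the only numeric trigger for non-fatal colitis, pneumonitis, hepatitis or rash. On its natural reading it covers 27% of planned combination treatment, leaving 246 days to discretionary review.

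This rests on two readings that the text does not settle: that the 90 days start at the first combination dose, and that they limit which events count toward the trigger. The size rests on assumed event rates, onset patterns and 12 to 24 combination patients. The change matters only if toxicity is both frequent and later in onset.

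**What to change.** In sections 4.1 and 8.5, replace the 90-day period in rule (b) with: *from the first combination dose until 30 days after the latest dose of ublituximab or umbralisib*. State that listed toxicities in that period count toward the halting rule. The toxicity list and the consecutive-patient threshold stay as they are.

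The cost is amendment wording in two sections. AEs are already collected to 30 days after the last dose (sections 7.3.7 and 8.3), and note 28 of the schedule of events already provides a clinic visit 4 weeks after combination treatment, so no visits or data are added. The downside is a slightly higher chance of a halt: in total 0.02% to 0.05% at the 7% rate with 12 to 24 combination patients.
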